2.4 Rationale of proposed fractionation scheme

The primary rationale for accelerated PMRT is the enhanced convenience for patients which may result in increased access to PMRT. With data now available documenting the low α/β ratio for breast cancer, the fraction sensitivity of breast cancer can be exploited with higher fraction sizes, resulting in more compressed treatment times. However, care must be taken to not exceed the tolerance of normal tissues. We propose delivering a chest wall dose of 36.63 Gy in 11 fractions of 3.33 Gy delivered over 11 days, 1 fraction per day. This fractionation should produce late effects and tumor control comparable to a conventionally fractionated course of 45-46 Gy. Patients may also receive a chest wall “scar” boost of up to 4 fractions of 3.33 Gy delivered once daily at the discretion of the treating physician. This boost fractionation should produce tumor control comparable to a 16 Gy conventional boost. This fractionation scheme has the benefit of delivering the entire treatment over 11-15 treatment days (weekdays only). The proposed fractionation scheme is compared to a conventional fractionation scheme of 2 Gy times 30 in 39 days⁷⁵.

Tumor control	α/β ratio	Standard schedule (2 Gy x 30)	Proposed schedule (3.33 Gy x 15)	Proposed schedule in 2 Gy equivalents
	4	90 Gy ₄	91.5 Gy ₄	61 Gy
	4	86 Gy ₄ *	91.5 Gy ₄	61 Gy
Normal tissue response ^{**}	α/β ratio	Standard schedule (2 Gy x 23)	Proposed schedule (3.33 Gy x 11)	Proposed schedule in 2 Gy equivalents
	3	77 Gy ₃	77 Gy ₃	46 Gy
	4	69 Gy ₄	67 Gy ₄	45 Gy

* Correcting for cell proliferation during the course of treatment

** These are for normal tissue effects within the whole breast volume of the standard schedule

3. Participating Institutions

4. Experimental Design and Methods

4.1 Duration of Study

Patients will be enrolled in this trial over the course of approximately 36 months. The duration of the protocol for each patient will be from the date of registration to the last day of radiation therapy. Patients will be followed regularly after treatment as per standard departmental policy (Section 9.2.1). The duration of the study is estimated to be 72 months, such that the minimum follow-up in the study cohort is 36 months.

4.2 Study Design

[figure not shown]
This study is a non-randomized, single arm study of female patients with early stage or advanced invasive ductal, lobular, medullary, papillary, colloidal (mucinous), or tubular carcinoma receiving accelerated chest wall irradiation following mastectomy.

A patient who is diagnosed with breast cancer will be seen by their surgeon for evaluation of their cancer, discussion of surgical management, and possible enrollment onto clinical trials, including this trial.

- The patient has 14-63 days from the date of last surgery or date of last chemotherapy cycle to register and undergo CT simulation. Then the patient has 21-63 days after the last surgery/last chemotherapy cycle to start radiation therapy.
- PMRT may be delivered before cytotoxic chemotherapy.
- If chemotherapy is delivered after radiation therapy, it must begin no earlier than 21 days following completion of radiation therapy.
- All patients will meet with a medical oncologist or medical oncology nurse prior to beginning RT.
- All patients will receive radiotherapy based on CT treatment planning.
- If the patient underwent a mastectomy at an outside facility, she will still be eligible for the trial if all other eligibility criteria are met.
- Hormonal therapy, if indicated, can be initiated before, during or after radiation at the discretion of the treating physicians.

[REDACTED]

4.2.1 Study Schema – Postmastectomy radiation therapy

If chemotherapy is indicated and is delivered after RT, it must start ≥ 21 days after completion of RT.

RT time = 11 weekdays (once/day) chest wall irradiation = 11 RT days

Total Elapsed Time = 11 total weekday RT = 15 elapsed days (mastectomy scar boost optional up to 4 fractions)

5. Study Enrollment Criteria

5.1 Inclusion Criteria

- 5.1.1 Invasive ductal, medullary, papillary, colloid (mucinous), or tubular histologies. Invasive lobular carcinomas are allowed.
- 5.1.2 AJCC Stage IIa – IIIc (pathologic stage T0N1-3, T1N1-3, T2N1-3, T3N0-3, T4N0-3, all M0 status) histologically confirmed invasive carcinoma of the breast treated with mastectomy and either sentinel node biopsy or axillary dissection. Inflammatory carcinoma (T4d) is allowed.
- 5.1.3 Patients with locally advanced breast cancer on clinical exam and diagnostics (> 3 cm and/or clinically node-positive) who have mastectomy after induction chemotherapy are allowed.
- 5.1.4 Multifocal/multicentric disease is allowed.
- 5.1.5 Negative inked histologic margins of mastectomy (no invasive cells at margin) or positive margin at pectoralis fascia or skin.
- 5.1.6 Tamoxifen, Arimidex or other hormonal therapy is allowed. It may begin any time relative to the radiation at the discretion of the treating physician.
- 5.1.7 Chemotherapy is allowed. If chemotherapy is indicated the chemotherapy can be delivered first, followed by radiation therapy beginning 21-63 days after the last cycle of chemotherapy or the radiation therapy can be delivered first and the chemotherapy can be delivered no earlier than 21 days post radiation therapy. Neoadjuvant chemotherapy is allowed; radiation therapy will be delivered after mastectomy or after any adjuvant chemotherapy as described above.
- 5.1.8 Chest wall reconstruction is allowed.
- 5.1.9 The patient must be enrolled and have treatment planning between 14 – 63 days from date of last surgery or last cycle of chemotherapy, and radiation must start within 21-63 days of date of last surgery or last cycle of chemotherapy.
- 5.1.10 Women must be \geq 18 years of age.
- 5.1.11 Signed study-specific informed consent form prior to study entry.
- 5.1.12 ECOG performance status of 0 or 1.

5.2 Exclusion Criteria

- 5.2.1 Patient with distant metastases (M1).
- 5.2.2 Patients with ductal or lobular carcinoma in-situ alone (no invasive component) and patients with non-epithelial breast malignancies such as sarcoma or lymphoma.
- 5.2.3 Patient with T1N0 or T2N0 disease.
- 5.2.4 Prior radiation therapy to the chest.
- 5.2.5 Patients with collagen vascular diseases, specifically systemic lupus erythematosis, scleroderma, or dermatomyositis.
- 5.2.6 Patients with co-existing medical conditions with life expectancy < 2 years.

- 5.2.7 Patients with psychiatric (with the possible exception of incompetence as defined by [REDACTED] or addictive disorders that would preclude obtaining informed consent).
- 5.2.8 Other malignancy, except non-melanomatous skin cancer, < 5 years prior to participation in this study; the disease-free interval from any prior carcinoma must be continuous.
- 5.2.9 Women who are pregnant or lactating due to potential exposure of the fetus to RT and unknown effects of RT to lactating females.
- 5.2.10 Women who are able to conceive and unwilling to practice an effective method of birth control. Women of childbearing potential must have a negative urine or serum pregnancy test within 7 days prior to treatment.

5.3 Inclusion of Women and Minorities

Women of all ethnic groups are eligible for this trial.

[figure not shown]
5.4 Participation of Children

Study participants must be over the age of 18 to be eligible for this trial.

5.5 Sources or Methods of Recruitment

Participants of this study will be recruited by the clinics of participating surgical, medical, and radiation oncologists in the [REDACTED]

5.6 Study Enrollment Procedures

Accelerated, Hypofractionated Chest Wall Radiotherapy in Women with Breast Cancer: A Phase II Trial
 [REDACTED]

6. Study Parameters

Evaluations	Prior to treatment	During Radiation (weekly)	FOLLOW-UP (after radiation therapy)		
			End of Radiation and 2-8 weeks after RT	Then every 3-9 months (for 3 yrs)	Then every 6-15 months (out to 5 yrs)
Signed informed consent	X				
History & Physical	X	X	X	X	X
Pregnancy test (B-HCG)	X ¹				
Chest wall CT (Simulation)	X ²				
Optional serum and tumor tissue samples	X ³				

1. Within 7 days before starting treatment if of child bearing age. For menopausal status, see Appendix C.

2. After surgery/chemotherapy for treatment planning

3. For optional correlative studies, patients will be offered co-enrollment in CINJ Study # 040703 (IRB 0220070169). See Sections 9.4 and 11.

4. End of radiation = During the last 3 fractions of radiation

7. Treatment Plan

Postmastectomy RT consists of 3663 cGy in 11 fractions (333 cGy) over 11 weekdays (for 15 elapsed days); no boost is required, optional chest wall boost upto 4 fractions of 3.33 cGy is allowed (total 1332 cGy).

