7.11 Anticipated Toxicity

Erythema and desquamation in the vicinity of the treated volume are anticipated to occur. Some patients may develop a moist desquamation, which usually heals within a few weeks. Cellulitis is rare, however. Fatigue is also to be expected. Toxicities will be recorded using CTCAE v 4.0 and attribution of AEs will be recorded.

7.11.1 **Toxicity Management:** Appropriate medical & skin care should be given according to standard practices per departmental guidelines.

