7.13 Supportive Care Guidelines

Patients are allowed to receive full supportive care therapies concomitantly during the study such as anti-emetics, skin care, and antibiotics. No other chemotherapy, immunotherapy, or experimental medications will be permitted while the patients are receiving radiation therapy. The use of hormonal cancer therapy during radiation therapy is allowed. Patients may be enrolled on other clinical trials if they do not conflict with the use of radiation therapy as described above.

8. Toxicity Monitoring and Adverse Event Reporting

All patients who receive one dose of protocol therapy will be evaluable for assessment of toxicity. Prior to each cycle the treating physician or their designee will fully assess the patient's condition with respect to possible treatment related toxicities. All adverse events Grade 2 or greater related to radiation therapy, whether observed by the physician or reported by the patient, occurring during the active portion of therapy, or up to 30 days after the last dose of treatment will be graded by a numerical score according to the National Cancer Institutes' (NCIs') Common Terminology Criteria for Adverse Events (CTCAE), Version 4.0 (<http://ctep.cancer.gov/reporting/ctc.html>) and recorded in the patient's medical record. Toxicities (including laboratory abnormalities) will be reported as outlined in the data capture plan.

A preexisting condition is one that is present at the start of the study. A preexisting condition will be recorded as an adverse event if the frequency, intensity, or the character of the condition worsens during the study period.

The Investigator will follow all patients who experienced an AE until there is a return to the patient's baseline condition or until a clinically satisfactory resolution is achieved.

8.1 Adverse Events.

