9.1 Toxicity

9.1.1 The Common Terminology Criteria for Adverse Events version 4.0 (CTCAE) (<http://ctep.cancer.gov/forms/CTCAEv4.pdf>) for acute toxicity of the skin will be used to score and report acute toxicity.

- ◊ Patients will be seen in follow-up weekly during treatment, at the end of radiation, then 2-8 weeks after RT, 3-6 months for 3 years, then every 6-12 months out to 5 years.

9.1.2 Additional toxicity end points:

[figure not shown]
- ◊ **Brachial plexopathy:** Investigators should record information relevant to brachial plexopathy at each follow-up visit, and include 1) method of detection, 2) signs & symptoms, and 3) method of treatment (see CRF in Appendix D).
- ◊ **Pain:** Information about pain should be recorded at each visit as documented in the CRF in Appendix D.
- ◊ **Pigmentation and Telangiectasia:** Information regarding skin pigmentation and telangiectasia will be recorded at each follow-up visit and graded I-IV (refer to CRF in Appendix D).

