
1. Complication Assessment (Must be evaluated at each visit)
 
 
 A Acute skin toxicity	 Not evident	 If Yes, complete CRF #3;	
 
 B Brachial plexopathy	 Not evident	 If Yes, complete CRF #4; Section I	
 
 C Acute lung toxicity	 Not evident	 If Yes, complete CRF #3;	
 
 D Pain	 Not evident	 If Yes, complete CRF #3&CRF #4; Section II	
 
 E Revision of plastic reconstruction	 Not evident	 If Yes, complete CRF #4; Section IV	
 
 F Fibrosis	 Not evident	 If Yes, complete CRF #3	
 
 G Other (Fatigue, Lung, Heart)	 Not evident	 If Yes, complete CRF #3&/or CRF#4,5 or 6	
 
 
2 Local failure:
 
 
  Scar	 Chest wall	 Inflammatory	 Biopsied	
 
 			 Invasive	
 
 			 Non-invasive	
 
 			 Grade _____	
 
 			 Receptor status _____	
 
 
3 Regional failure:
 
 
  Axilla	 Supraclavicular fossa	 Internal mammary nodes	 Skin	 Other	
 
 
4 Distant Failure
 
 
  Lung	 Bone	 Other	
 
				A Acute skin toxicity	 Not evident	 If Yes, complete CRF #3;	B Brachial plexopathy	 Not evident	 If Yes, complete CRF #4; Section I	C Acute lung toxicity	 Not evident	 If Yes, complete CRF #3;	D Pain	 Not evident	 If Yes, complete CRF #3&CRF #4; Section II	E Revision of plastic reconstruction	 Not evident	 If Yes, complete CRF #4; Section IV	F Fibrosis	 Not evident	 If Yes, complete CRF #3	G Other (Fatigue, Lung, Heart)	 Not evident	 If Yes, complete CRF #3&/or CRF#4,5 or 6	 Scar	 Chest wall	 Inflammatory	 Biopsied				 Invasive				 Non-invasive				 Grade _____				 Receptor status _____	 Axilla	 Supraclavicular fossa	 Internal mammary nodes	 Skin	 Other	 Lung	 Bone	 Other

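### Acute toxicity can peak and heal between visits: the first post-treatment visit may be as late as day 56, and CRF #3 records neither event dates nor a worst grade

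*Combined protocol and SAP*

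**What the plan says.** **Visits.** The evaluation table in Section 6 gives one column for "End of Radiation and 2-8 weeks after RT". Its footnote fixes the first half of that column: "End of radiation = During the last 3 fractions of radiation". Section 9.1.1 repeats the schedule as "at the end of radiation, then 2-8 weeks after RT, 3-6 months for 3 years". The two places agree on the first post-treatment window.

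**Recording period.** Section 8 requires related adverse events of grade 2 or above to be graded, "whether observed by the physician or reported by the patient", when they are "occurring during the active portion of therapy, or up to 30 days after the last dose of treatment". They are written in the medical record.

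**Expected course.** Section 7.11 says of skin reactions: "Some patients may develop a moist desquamation, which usually heals within a few weeks".

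**Forms (Appendix D).** CRF #2 is headed "Complication Assessment (Must be evaluated at each visit" and offers, for each complication, either absence or a pointer to another form. Acute skin and acute lung toxicity point to CRF #3 only. CRF #3 has the visit date, grade columns and a comments column. CRF #4 has onset and resolution dates for brachial plexopathy, pain, telangiectasia and reconstruction revision.

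**Use of the data.** Acute toxicity is listed under the primary endpoint (1.1.1) and scored by CTCAE (9.1.1). The event counted in Section 16.2 is made up of grade 3 or higher chest wall pain, symptomatic brachial plexopathy, and grade 3 or higher acute symptomatic pneumonitis.

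**The concern.** The end-of-radiation check is an on-treatment check, so the first assessment after the last fraction is the single visit at 2-8 weeks. The base course lasts only 15 elapsed days, so weekly on-treatment review is brief and later reactions depend on that one visit. If it falls late, a reaction the protocol expects to heal in weeks may already be gone. The acute form then has no field to recover how bad it was or when it happened.

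Two things are at stake. The recorded acute grade may be lower than the true peak. And an event mentioned at a late visit cannot be assigned to the inside or outside of Section 8's 30 days, so the acute-toxicity rate would rest on undated recall.

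**Working it through.** The plan gives no calculated figure on this point. For context, the Section 16.2 rule (5 or more events among 67) reproduces by exact binomial tails: P(X ≥ 5 | 67, 0.03) = 0.0508 and P(X ≥ 5 | 67, 0.09) = 0.7316, against the stated 0.0508 and 0.732.

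**1. Visit window against recording period.**
- Earliest visit: 2 × 7 = day 14. Latest: 8 × 7 = day 56 (Sections 6 and 9.1.1).
- Recording period ends on day 30 (Section 8).
- Latest visit minus end of period: 56 − 30 = 26 days.
- Share of the permitted window after day 30: 26 / (56 − 14) = 26/42 = 0.62.
- An early visit does not cover the period either. A visit on day 14 leaves 30 − 14 = 16 days of it to the next visit, months later.

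**2. On-treatment review.** The base course gives 15/7 = 2.1 weeks of weekly review. With the optional boost, 19 elapsed days (Section 7.6) give 19/7 = 2.7 weeks.

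**3. Healing before the visit.** Section 7.11 gives no number of days, so healing time has to be assumed. If a reaction has healed by day 28, (56 − 28)/42 = 0.67 of permitted visit days come after healing; if by day 42, (56 − 42)/42 = 0.33.

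**4. What each form can recover.**

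| Item | Form | Onset and resolution dates | Worst grade since last visit |
|---|---|---|---|
| Acute skin reaction | CRF #3 | No | No |
| Acute lung toxicity | CRF #3 | No | No |
| Pain | CRF #3 and CRF #4 | Yes, on CRF #4 | No |
| Brachial plexopathy | CRF #4 | Yes | No |

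CRF #3 also has no row named pneumonitis; its respiratory rows are bronchospasm, cough, dyspnea and voice changes.

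**5. Sensitivity of the Section 16.2 rule (illustration only).** If a fraction m of all primary events went unrecorded, the effective rate at a true 9% would be 0.09 × (1 − m). For m = 10%, 25% and 50% this is 0.081, 0.0675 and 0.045. The chance of reaching 5 events falls from 0.73 to 0.64, 0.48 and 0.18. The documents give no value of m, and only one component of the event depends on CRF #3 with no dated record elsewhere.

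**The case against.** The strongest case against has four parts.

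- **Section 8 limits when an event occurs, not when it is written down.** A reaction on day 20 that is elicited on day 45 still qualifies. This stands. It also shows why dates matter: without an onset date on CRF #3, nobody can tell that the event was on day 20.
- **Other safeguards exist.** Patient-reported events count, the 2-8 week visit includes a history and physical, and patients with a known event are followed until it resolves. These narrow the gap. They do not ensure that a peak grade or a date reaches the form.
- **The primary event is mostly outside the problem.** Skin reaction is not part of it, and pain and plexopathy have dates on CRF #4. CRF #2 asks about the lung at every visit and can also route to CRF #6. This stands, except that CRF #6 is a late-toxicity scale with a visit date only, so acute pneumonitis remains undated.
- **Appendix D may not be the whole data capture.** Sections 8 and 13.1 refer to a data capture plan and electronic forms that are not in the documents. If those already hold the fields, the forms part of the point falls away.

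A reader might infer three stronger things that the documents do not support. First, that events seen after day 30 are lost, or that 62% of them are: the figure counts permitted visit days, not patients or events. Second, that the gap biases results in favour of the short course: Section 17.4 gives 42 calendar days for the conventional course, but nothing says how the published series timed or scored acute reactions. Third, that the 5-of-67 rule loses the power shown in the illustration: that assumes loss across all components, at rates the documents do not give.

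**Conclusion.** The point holds in limited form. A fully compliant site may have no scheduled contact between the last fractions and day 56, which is 26 days after Section 8's limit. CRF #3 cannot then recover the peak grade or date of an acute skin or lung reaction. The main effect is on the acute-toxicity objective (1.1.1 and 9.1.1). Of the Section 16.2 event, only grade 3 or higher acute symptomatic pneumonitis is exposed.

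Neither the size of any under-grading nor its direction relative to published long-course results can be derived from the documents. The conclusion assumes that Appendix D reflects the fields in use, and that some reactions heal within the permitted visit window, which Section 7.11 makes plausible but does not quantify. It is a cheap improvement in data capture, not a flaw in the primary test.

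**What to change.** - On CRF #3, and in the matching CRF #2 prompts, record for each acute item the worst CTCAE grade since the previous visit, with onset and resolution dates. CRF #4 is a precedent for the dates, though not for the worst grade.
- Reconcile the first post-treatment visit window in Sections 6 and 9.1.1 with the 30-day period in Section 8, so that each patient has one scheduled assessment that covers that period. Moving the visit earlier is not enough alone, because a day-14 visit leaves 16 days uncovered.

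The cost is three fields on existing forms and one edit to the windows, with no extra visit. The drawbacks are some recall error in the worst grade and a tighter visit window for sites.

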7.1 Equipment

◊ External beam radiation therapy

- Modality: Any combination of photon beams of energy 6 MV or higher, with or without the addition of electrons of any energy, may be used for treatment provided the dosimetric requirements of adequately treating the planning target volume and dose homogeneity are met. Proton therapy, IMRT, tomotherapy, and other highly conformal external beam techniques are allowed.
- Energy: Minimum of 6 mV photon or equivalent.

7.2 Imaging

- ◊ CT treatment planning is mandatory. Commercially available software for 3-D treatment planning should be used for treatment planning. The treatment planning CT scan should include the entire breast. A CT scan thickness of \leq 3 mm is required. The patient's position should be reproducible and comfortable, and must be supine.

7.3 Planning Target Volume

7.3.1 PTV for the chest wall RT will include all tissue within the boundaries of standard chest wall tangential fields, excluding lung, heart and any non-chest wall structures within the volume (e.g. rib, liver). A formal PTV contour is not mandatory but is encouraged. Standard tangential fields will be set as is routine practice for the treating radiation oncologist, using medial and lateral skin wires for the tangent borders. However, no greater than 3 cm of lung should be visible at any level of the tangent beam. Collimation is not allowed if a third or fourth field (suprACLAVICULAR field/PAB) is matched to the tangents. In this case, the tangents must be designed with a nondivergent cranial edge perfectly matched to the third/fourth fields. The determination for adding a third or fourth field is left to the discretion of the treating radiation oncologist, but is typically used for the majority of patients with indications for PMRT.

7.4 Dose limitations for normal tissues

- ◊ The perpendicular distance from the chest wall to the posterior field edge can include at maximum 3 cm of lung tissue at any point along the length of the tangent.
- ◊ For left-sided cancers, the heart should be blocked from the primary beams as long as the 90% isodose line is covering the intended target volume.
- ◊ Dose to the brachial plexus should not exceed 107% of prescription dose.

7.5 Treatment Dose

Postmastectomy chest wall will get 3663 cGy in 11 fractions; a scar boost is optional at the discretion of the treating physician, upto 1332 cGy in 4 fractions. Treatment may be started on any weekday, and will not be given over holidays or weekends.

- ◊ **Prescription Point**

7.5.1 Dose from the chest wall fields can be prescribed at a point 1.5 cm anterior to the posterior edge of the fields at mid-separation, or to a point 1/3rd the distance from this point to the skin, or to an isodose line encompassing the PTV. IMRT technique and other highly conformal techniques are allowed.

